### **IV. SUBJECT ENROLLMENT**

For this study, we will use a newly developed TopCare smoking and lung screening registry. The registry uses the data from patient's EMR regarding the smoking history and imaging (most recent chest CT) and it is daily

updated. We will choose the current smokers age 55-77 from the registry who did not have chest CT in the last year receiving care at MGH health centers. We will e-mail primary care providers a list of their patients and ask them to notify us in a week if they do not want us to contact a patient and to provide a reason why they believe patient is not eligible for lung screening. Patients meeting eligibility criteria for the study according to the criteria above will be identified and randomly assigned to navigation or control group. An electronic list of patients assigned to the intervention group will be downloaded into an existing TopCare navigator data base. The navigators will use this system to track patients and record interventions. Patients randomized to the intervention group will be recruited by navigators during their visits to the health center or over the phone. Since the navigator program is already standard of care at MGH, its expansion to include lung screening is considered part of usual care.

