The patients in the intervention group will be mailed a letter about the program in English or Spanish with educational materials about lung screening following randomization and prior to any contact by the PN. A week later, the PN will contact patients over the phone or in person during office visits. For patients that speak languages other than English or Spanish, this initial contact with the PN will be aided by an interpreter. The interpreter will review the recruitment letter and Fact Sheet with the patient and ask the patient if they are interested in continuing with the research study. During this initial contact, the PN will obtain a detailed history to determine if the patient is eligible for lung screening. The PN will educate patients about lung screening and explore their barriers to screening. The PN will coordinate scheduling a shared decision appointment with a provider and, whenever feasible, attend the visit with the patient. The PN will further coordinate scheduling the lung screening test if the provider and patient made that decision and navigate the patient to obtain the test. Interventions may include: reminding the patient about the test, helping with translation, insurance issues, transportation, and overcoming any other system barriers as needed. After screening, PN will review the results. If the patient has an abnormal test result, the navigator will contact the patient's primary care physician and help the patient obtain required follow-up.

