#### **V.4. Randomized Clinical Trial (Specific Aim 2)**

To test our hypothesis we will randomize eligible patients receiving care at CHCs to one of two study groups:

Early intervention	Usual care/delayed intervention
400 patients will receive 1:1 PN to obtain lung screening and follow-up of abnormal results, as well as smoking cessation guidance	800 patients will receive usual care during the 1-year study period. After the study period they will be offered 1:1 PN to obtain lung screening and follow-up of abnormal results as well as smoking cessation guidance

Eligibility criteria:

1. Inclusion criteria: adult patients aged 55-77 years who are current cigarette smokers (according to an algorithm using EMR data), and receive care at one of the five MGH CHCs.
2. Exclusion criteria: 1) patients who have previously received a diagnosis of lung cancer per EMR, 2) have undergone a chest CT within 18 months before enrollment, 3) are subsequently identified as having died prior to the study intervention 4) deemed by their primary care provider as not eligible for lung screening

Patients will be identified using existing electronic systems developed by the MGH Primary Care Operations Improvement (PCOI) program (Protocol # 2004P002796).

Using a newly developed TopCare smoking and lung screening registry, we will identify smokers receiving care at MGH health centers who could be eligible for lung screening. We will e-mail primary care providers a list of their patients and ask them to notify us in a week if they do not want us to contact a patient and to provide a reason why they believe patient is not eligible for lung screening. The eligible patients will then be randomly allocated to the intervention or usual care groups. Patients randomly assigned to the intervention group will be eligible for PN, while patients randomly assigned to the control will receive usual care and be eligible for navigation after the one year period.

Patient navigator intervention:

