PN program delivery: A letter about the program with lung screening educational materials used in usual clinical practice will be mailed to eligible patients. A week later, the PN will contact patients over the phone or in person during office visits. The letters will be sent in stages. First, PN will use TopCare IT system to identify patients who have appointment scheduled and send letters/contact them prior to their appointments. Patients who do not have appointments scheduled will be contacted in stages so that during the first 6 months of the study all eligible patients receive a letter and at least one phone call attempt from PN. During the initial contact, the PN will obtain detailed history to determine if patient is eligible for lung screening. The PN will educate patients about lung screening and explore any barriers to screening. If the patient is interested in screening, the PN will coordinate scheduling a shared decision-making appointment with a provider and, whenever feasible, attend the visit with the patient. The PN will further coordinate scheduling the CT scan if the provider and patient made that decision and navigate the patient to obtain the test. Further interventions may include:

reminding the patient about the test, helping with translation, insurance issues, transportation, and overcoming any other system barriers as needed. After screening, the PN will review the results. If the patient has an abnormal test result, the navigator will contact the patient's primary care physician and help the patient obtain required follow-up.

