### VI.2 Secondary outcomes

1. Percentage of patients who had at least one chest CT (according to billing and EMR data) during the 1-year study period, comparing patients contacted by patient navigator in the intervention group ("as treated" analysis) vs. all patients in control group.
2. Percentage of patients in intervention vs. control groups who had at least one lung CT screening stratified by language spoken, race, age (<> 65 years) and practice site. (subgroup analysis)
3. Of patients whose initial chest CT generated a radiologist's recommendation for early interval follow-up, the percentage who received the recommended follow-up of in timely manner. The timeliness of care is defined by radiologist's recommendation plus additional 30 days. For recommended biopsy/PET scan we chose 60 days limit. All radiologists at MGH use Lung-RADS system to recommend the follow up post LDCT. These standardized recommendations include 12, 6 or 3 months follow up or for suspicious malignancy PET CT vs biopsy. There is some variability in reading diagnostic chest CT; however recommendations are similar to Lung-RADS. At the end of one-year trial a blinded research assistant will review the electronic medical records of patients who had a chest CT during study period. The dates of imaging will be confirmed by billing data.
4. Mean time to follow-up of abnormal results, comparing intervention and control groups.
5. Tobacco treatment use: Percentage of patients, comparing intervention and control groups, who during the 1-year study period had any of the following:
  - o referral to MA Quitline as determined by patients' QuitWorks data or referral scanned in EHR
  - o smoking cessation medication prescribed in EHR (nicotine patch, gum, lozenge, inhaler, nasal spray or bupropion, or varenicline) during the study period
  - o referral to in-person counseling from CHC-based tobacco coach –documented in EHR
6. Percentage of patients, comparing intervention and control groups, who have a status of former or nonsmoker entered in coded field of EHR at the visit closest to the date of 1 year follow-up.
7. Percentage of patients in intervention group who are reached by PN and percentage of patients reached who had lung screening (process measures)

## AIM 3

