## **VII. RISKS AND DISCOMFORTS**

We see no significant risks to patients as a result of this study. Patients the intervention group will be contacted by a culturally competent PN who will assess their interest in lung screening. For some individuals this information may cause distress if it is something they are not interested in doing or if they do not think it accurately reflects their particular situation. This information may also not be up to date for all patients. If an individual believes this is the case, he/she will be provided information about whom to contact to update their records. A standard system is in place as part of usual care to input this information into the patient's electronic medical record to communicate this information. All contact with patients, including those in the control group, will be based on current MGH Primary Care guidelines for usual care.

Specific Aim 4: There are no foreseeable risks from participating in this quantitative interview study except the time commitment required and the possibility of psychological discomfort in discussing the subject of cancer prevention. Demographic information will be obtained from electronic medical record. All data will be stored on password-protected computers. Personal health information will be de-identified during data collection. All identifying patient information will be deleted prior to analysis and data will only be presented in aggregate.

Specific Aim 5: There are no foreseeable risks from completing this survey. No personal or demographic information will be collected. Providers may decline to complete the survey if they wish.

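### Outcome 6 cannot tell a quit during the trial from a late correction of the smoking record, and navigator contact can make such corrections more frequent in one arm

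*Combined protocol and SAP*

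**What the plan says.** **Entry.** Section V.4 (inclusion criterion 1) admits "current cigarette smokers (according to an algorithm using EMR data"). Section IV describes the source: "The registry uses the data from patient's EMR regarding the smoking history and imaging". It is refreshed daily. Before randomisation, primary care providers receive a list of their patients and have a week to object and say why a patient is not eligible for lung screening. No step asks the patient about current smoking before randomisation.

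**Currency of the records.** Section VII, describing navigator contact in the intervention group, says "This information may also not be up to date for all patients". A patient who thinks so is told how to have it changed: "he/she will be provided information about whom to contact to update their records". The same paragraph adds: "A standard system is in place as part of usual care to input this information into the patient's electronic medical record".

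**Contact by arm.** In the intervention arm, section IV has it that "the PN will obtain a detailed history to determine if the patient is eligible for lung screening", and section V.4 repeats this. The navigator also asks about interest in quitting. Control patients receive usual care for the year.

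**Outcome and test.** Section VI.2, item 6, scores patients "who have a status of former or nonsmoker entered in coded field of EHR" at the visit nearest one year. Section VI.3 compares the arms by chi-square and calls the variable documented smoking status. Neither section asks for a quit date, a quit after randomisation, or any confirmation.

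**The concern.** A patient who stopped smoking before randomisation but is still coded as a current smoker is misclassified at entry. Randomisation balances these patients between the arms. It does not balance how often their records are put right afterwards, because one arm has a person asking about smoking and pointing to the correction route and the other does not. Item 6 scores each correction exactly as it scores a quit. If nonsmoker includes never-smokers, that code in someone enrolled as a current smoker can only be a correction.

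At stake is the reading of the only outcome in the plan that reflects smoking status itself. Section V.1 says the navigator will help patients stop smoking and section VIII lists cessation as a possible benefit, so a difference in item 6 invites a cessation reading. A larger sample would not remove the bias.

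**Working it through.** **Is there a figure of the plan's to reproduce?** No. The only power statement (section VI.4) concerns lung screening. The documents give neither a rate of outdated records nor correction rates, so the size can only be shown as a range over assumptions.

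**Inputs from the documents**
- Arm sizes 400 and 800 (section V.4). Section VI.4 has a total of 1276, which implies 1276 − 400 = 876 controls; see the last step.
- Share of the intervention arm reached: 300/400 = 0.75 (section III).
- Alpha 0.05 (section VI.4), taken as two-sided.

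**Assumed inputs**
- q = 8%: share of each arm coded former or nonsmoker because of true quitting, equal in both arms.
- m = 2%, 5% or 10%: share whose record was already outdated at randomisation.
- c = 25%: share of those records corrected through usual care in either arm.
- k = one-third to 75%: share of the remaining outdated records corrected among reached patients. Arm-wide this is x = 0.75 × k, so x = 0.75 × 1/3 = 0.25 up to 0.75 × 0.75 = 0.5625.

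**Formulas**
- Control: p0 = q + m·c
- Intervention: p1 = q + m·c + m·(1 − c)·x
- False difference: D = m·(1 − c)·x = 0.75·m·x
- Rejection probability: Φ[(D − 1.96·SE0)/SE1] + Φ[(−D − 1.96·SE0)/SE1], with SE0 from the pooled proportion and SE1 from the separate proportions.

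**Results, no true effect on quitting, 400 vs 800**

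| m | p0 | p1 | D (points) | Chi-square rejects |
|---|---|---|---|---|
| 2% | 8.50% | 8.88–9.34% | 0.4–0.8 | 6–8% |
| 5% | 9.25% | 10.19–11.36% | 0.9–2.1 | 9–22% |
| 10% | 10.50% | 12.38–14.72% | 1.9–4.2 | 17–56% |

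**One cell in full** (m = 10%, x = 0.5625). D = 0.10 × 0.75 × 0.5625 = 0.0422. The pooled proportion is (400 × 0.1472 + 800 × 0.105)/1200 = 0.1191. SE0 = √[0.1191 × 0.8809 × (1/400 + 1/800)] = 0.0198. SE1 = √[0.1472 × 0.8528/400 + 0.105 × 0.895/800] = 0.0208. Then (0.0422 − 1.96 × 0.0198)/0.0208 ≈ 0.16, and Φ(0.16) ≈ 0.56; the second term is negligible.

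**Two checks.** With m = 0 the difference is 0 and the error rate is the nominal 5%. With 876 controls the last cell moves only from 56% to 58%.

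**The case against.** The strongest reply has four parts.

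1. *The text on correction is passive and not expressly about smoking.* Section VII only tells a patient who disagrees whom to contact, and it does not say which information may be outdated. This stands as a limit on certainty. But patients are selected for contact on EMR age, smoking and chest CT data, so smoking status is the natural reading. Section II also defines screening eligibility by pack-years and time since quitting, so an eligibility history has to cover it.

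2. *Controls can be corrected too, and entry is screened.* Usual care has an updating system, the registry is refreshed daily, and providers review their lists before randomisation. All of this stands. It lowers the share of outdated records and narrows the gap between arms. It does not close the gap, because navigator contact is added to usual care in one arm only.

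3. *The plan already calls the variable documented status.* True of section VI.3, and Aim 2 speaks of use of cessation services rather than quitting. The fault lies in a cessation reading, which the plan does not rule out.

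4. *The size rests on assumptions.* It does. At 2% outdated records the effect is close to nil.

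A reader might infer more than the documents support:
- That item 6 is certain to favour navigation falsely. The text supports only that it can.
- That smoking status is re-coded at the shared decision visits. No section says so, and in section V.4 those visits are arranged only for patients interested in screening.
- That the error must be large. With 15% outdated and 80% corrected among reached patients against 20% otherwise, the difference is 0.15 × 0.75 × 0.60 = 6.75 points, but nothing in the documents favours those inputs over the near-null ones.

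**Conclusion.** The concern holds as a possible bias of known direction and unknown size. As written, item 6 can favour navigation with no additional quitting, because it does not separate quits before randomisation from quits after it and the chance of correction differs by arm. Over the assumed range of 2% to 10% outdated records, the false difference runs from about 0.4 to 4.2 points and the rejection rate from about 6% to 56%, against a nominal 5%. These figures depend on the assumed 8% quit rate, the 25% usual-care correction and the correction rate among reached patients. Only the arm sizes, the alpha and the 75% reach come from the protocol.

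The consequence is confined to one of seven secondary outcomes. The chest CT primary outcome is not touched by this mechanism. The change is worth making before analysis because it needs mainly a definition.

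**What to change.** - **Main rule.** For any cessation reading of item 6, count a change to former smoker only where the EHR shows quitting after the randomisation date. Use the same EHR source and rule in both arms. Quit dates from the navigator log must not define the outcome, since they would exist in one arm only.
- **Never-smoker recodes.** Count these as baseline corrections, not quits, and report them by arm.
- **Unrestricted figure.** Keep it, labelled documented smoking status as in section VI.3.
- **Sensitivity analysis.** Reset to current smoker those intervention patients whom the navigator recorded at first contact as having already quit. State that this is a conservative bound, because controls cannot be reset in the same way. At 10% outdated and 25% usual-care correction, controls keep 0.10 × 0.25 = 2.5 points of corrections. The reset then biases against navigation by 0.75 × 2.5 = 1.9 points if only reached patients are reset, and by 2.5 if all are. First contact may come some months after randomisation, so some quits made in between may also be reset, which adds to the conservatism.

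**Cost.** SAP wording, and a check that the navigator log captures smoking status at first contact; section V.4 requires information on every patient contacted but does not list this item. True quits without a date are lost in both arms. The documents do not mention a coded quit date in the EHR, so its availability must be confirmed. If there is none, report item 6 only as documented status, with the conservative bound beside it.

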### Outcome measure

Percentage of current smokers aged 55-77 years at baseline who have a chest CT in the subsequent 1 year, comparing patients receiving care at CHCs with patients from all other practices within the MGH primary care network.

### **VI.3. Analytic Methods**

#### **AIM 2:**

We will examine differences in lung screening rates using chi-square tests.

The comparisons include (1) between intervention and control groups (intention-to-treat analysis), and (2) between patients contacted and not contacted by patient navigators (“as-treated” analysis).

An exploratory subgroup analysis will compare lung screening rates between intervention and control groups stratified by language spoken, race, age (<> 65 years), practice site and other factors.

Furthermore, we will use logistic regression models to examine predictors of lung screening, including patient, provider, and practice characteristics.

In addition to comparing the percentage that completed recommended test in a timely manner between intervention and control group using a chi-square test, we will use survival analysis techniques to compare time to completion between intervention and control groups.

We will also use chi-square tests to compare the percentage with referral to MA Quitline, prescription to smoking cessation medications, referral to in person counseling from CHC tobacco coach, and documented smoking status in EHR between intervention and control groups.

For the intervention group, we will document process measures (percentage reached by PN and percentage agreed to have lung screening test within) and present with 95%CI's.

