## **V. STUDY PROCEDURE**

### **V.1. Overview**

We propose to develop, implement, and rigorously evaluate a novel lung screening patient navigator program for patients that currently smoke in five community health centers affiliated with a primary care network of a large academic hospital.

Eligible patients will include those receiving care in community health centers who are 55-77 years old and currently smoking. The intervention trial will be randomized at the patient level. In the intervention group, patients will be contacted by a culturally competent PN who will help them stop smoking and obtain lung screening. The control patients will receive usual care. The primary outcome will assess the percentage of eligible patients in intervention and control groups who had at least one chest CT during the study period. Secondary outcomes will include as-treated primary outcomes among intervention patients contacted by the patient navigator, primary outcomes stratified by language spoken, race, age, and practice site, follow-up of abnormal results, percentage of patients with tobacco treatment, and comparison of lung screening to other practices in the primary care network.

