### **VI.4. Sample Size Calculations**

We hypothesize that the navigator program will increase lung screening in the intervention group by at least 5%. With a total sample size of 1276 smokers, 400 randomized to the intervention group, and an alpha level of 0.05, we will have 88% power to detect a 5% difference. From our prior experience, a full time navigator with the assistance of two part-time interpreters/navigators can reach about 400 patients over nine months. Since our intervention includes follow-up of abnormal results, our study will last 1-year.

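### The primary comparison is an unadjusted chi-square with no confidence interval planned, and no stratification of allocation by health center is specified: a small, nearly free gain in efficiency is left unused

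*Combined protocol and SAP*

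**What the plan says.** Section V.1 sets the unit of allocation: "The intervention trial will be randomized at the patient level". Section V.4 adds only that "The eligible patients will then be randomly allocated to the intervention or usual care groups". Neither these sections nor Section IV describes strata, blocks or a method of generating the sequence.

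Section VI.3 (AIM 2) gives the primary analysis: "We will examine differences in lung screening rates using chi-square tests", with the first comparison "between intervention and control groups (intention-to-treat analysis". No covariate or stratum is named. Elsewhere in Section VI.3, language, race, age (cut at 65) and practice site appear as exploratory subgroup factors. Logistic regression is planned to look for predictors of screening, and is not described as an adjusted estimate of the arm effect. Confidence intervals are promised for the navigator process measures only.

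Inclusion requires age 55 to 77 and that patients "receive care at one of the five MGH CHCs" (Section V.4), so CHC and age are known for everyone before allocation.

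**The concern.** If chest CT use varies by health center or age, a test that uses those variables is somewhat more precise than one that does not, and stratified allocation keeps each center near its planned share of each arm. Both need only data already in hand. The trial is powered on a difference of 5 points, yet the plan does not commit to an interval around that difference. An adjusted arm effect drawn later from the open-ended predictor models would look post hoc. At stake are a little power and a clearer primary result.

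**Working it through.** **Inputs.** Section VI.4: "With a total sample size of 1276 smokers, 400 randomized to the intervention group", hence 1276 − 400 = 876 controls; and "an alpha level of 0.05, we will have 88% power to detect a 5% difference", taken as 5 percentage points, two-sided. Section V.4 has a smaller control arm: "800 patients will receive usual care during the 1-year study period". The control rate, the CHC sizes and the association of CHC or age with chest CT are not given. They are assumptions below.

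**Step 1: the plan's own power.** Power = Φ[(d − 1.96·SE0)/SE1], where SE0 uses the pooled rate and SE1 the separate rates. Assume 5% in controls and 10% in the intervention arm, with 400/876:

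- pooled rate = (40 + 43.8)/1276 = 0.0657
- SE0 = √[0.0657 × 0.9343 × (1/400 + 1/876)] = 0.01495
- SE1 = √[0.10 × 0.90/400 + 0.05 × 0.95/876] = 0.01671
- (0.05 − 1.96 × 0.01495)/0.01671 = 1.239, so power is 89.2%

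Exactly 88% needs a control rate of about 5.3%. With 400/800, a 5% control rate gives 88.3%. The stated figure is therefore attainable and implies a control rate near 5%. At 10% (400/876) power is 72.3%.

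**Step 2: what adjustment adds.** If baseline covariates explain a share R² of outcome variance, both standard errors shrink by √(1 − R²). At a 5% control rate with R² = 5%, SE0 = 0.01457, SE1 = 0.01629, the ratio is 1.317 and power is 90.6%.

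| Control rate (400/876) | Unadjusted | R² 1% | R² 2% | R² 5% | R² 10% |
|---|---|---|---|---|---|
| 5% | 89.2% | 89.5% | 89.8% | 90.6% | 91.9% |
| 10% | 72.3% | 72.7% | 73.2% | 74.4% | 76.6% |

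**Step 3: how large R² might be.** For five equal sites, R² is the variance of the site rates divided by p(1 − p). Site rates of 3.5% to 7.5% in one-point steps give 0.0002/(0.055 × 0.945) = 0.4%. Rates of 2% to 18% in four-point steps give 0.0032/(0.10 × 0.90) = 3.6%. Simulated power with site alone (10,000 runs per case, 400/876, Monte Carlo error about 0.3 to 0.45 points):

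| Assumed site rates | Chi-square, simple allocation | Mantel-Haenszel, simple | Mantel-Haenszel, stratified |
|---|---|---|---|
| 3.5% to 7.5% | 88.1% | 88.0% | 87.7% |
| 1.5% to 9.5% | 87.9% | 88.1% | 88.4% |
| 5% to 15% | 71.7% | 72.2% | 73.5% |
| 2% to 18% | 72.3% | 73.7% | 74.2% |

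Type I error was 4.5% to 5.3% in all simulated cases. The 4.5% came from the unadjusted chi-square after stratified allocation (site rates 2% to 18%), where Mantel-Haenszel gave 4.9%.

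Further simulations of 4,000 runs (400/800, control rate about 9% to 10%) assumed a site spread of ±0.6 to 0.8 log-odds and one more covariate worth 0.5 to 0.8 log-odds per SD. Power rose from 72.6% to 74.0% in one case and from 76.5% to 79.8% in the other. Null rejection was 4.2% unadjusted and 4.1% adjusted.

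**Step 4: chance site imbalance.** Take five CHCs of 240 patients (assumed), with 400 of 1200 drawn at random. The SD of one site's intervention share is √[(1/3)(2/3)/240 × 960/1199] = 2.7 points. The exact hypergeometric chance that a site is off its one-third share by more than 5 points (over 12 patients) is 5.5%; by 5 points or more, 7.8%. Over 200,000 random draws, at least one of the five sites was that far off in 23% and 31% respectively.

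The effect is small. A site 5 points over sends 92/400 = 23.0% to one arm and 148/800 = 18.5% to the other, a gap of 4.5 points. If its CT rate were 8 points above the rest (assumed), the estimate would move by 0.045 × 8 = 0.36 points. The standard error at 15% against 10% is √(0.15 × 0.85/400 + 0.10 × 0.90/800) = 2.1 points.

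**Step 5: room for covariates.** At 5% against 10%, expected events are 400 × 0.10 + 800 × 0.05 = 80 (83.8 with 876 controls). Arm, four CHC terms and age make six terms, about 13 events each. Multi-level race and language would thin this further.

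**The case against.** The strongest reply is that an unadjusted chi-square after patient-level randomization of 1200 to 1276 people is valid, standard and easy to read. That stands. Chance site imbalance is already allowed for in its error rate, and Step 4 shows how little it moves the estimate.

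A reader might infer that allocation was unstratified. The documents are silent, which is not the same thing: they neither state nor exclude strata.

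A reader might also infer a material loss of precision. That needs strong covariates and a 9% to 10% control rate, neither of which is in the documents. The stated power implies a rate near 5%, where site alone gave about half a point at most. The gains exceed 3 points only with R² near 10% or the most favourable simulation. The control rate matters far more: power at 400/876 is 89% at 5%, 72% at 10% and 52% at 20%.

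It is fair, too, that the percentages by arm are the outcome, so the point estimate is available; only its interval is unplanned. The subgroup and predictor analyses do use these variables, but neither is a pre-specified adjusted arm effect. Finally, adjusting for everything would not be free: a model with race, language and sex would be sparse and would need rules for missing or pooled categories.

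**Conclusion.** The point holds as a minor, nearly free improvement and not as an error. The primary test is unadjusted, no interval is planned for the primary difference, and no stratification is specified although CHC and age are in hand. Adjustment is worth about 0 to 3 points of power for assumed control rates of 5% to 10%, nearer 0 to 1.5 points if CHC and age explain a few percent of outcome variance and the control rate is near 5%. Type I error stays close to 5% either way.

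The documents do not support reading the chi-square result as biased or the stated 88% as wrong. The size of the gain rests wholly on assumed control rates, equal site sizes and covariate strengths. The benefit that does not depend on them is a planned interval and a clear account of how allocation is done.

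**What to change.** In Section V.4, specify computer allocation stratified by CHC, keeping the planned ratio within each center, and reconcile the control count with Section VI.4 (800 against 876).

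In Section VI.3, choose one primary analysis in advance:

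- a Mantel-Haenszel test stratified by CHC and age (under 65, 65 and over), with the stratified risk difference and its 95% CI; or
- a logistic model with arm, CHC and age only, with the standardized risk difference and its 95% CI.

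The first is the simpler choice with few events. Keep the unadjusted chi-square as a supporting result, and leave race and language to the planned subgroup analyses.

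The cost is a few sentences and one stratum variable in the allocation step. No extra patients, visits or data are needed. If allocation has already been made, state how it was done and adopt the analysis part alone before outcomes are examined.
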